3.5. Patient status

3.5.1. Study disposition

Recruitment status and patient discontinuation from study including reasons for discontinuation will be summarized by treatment arm.

3.5.2. Baseline demographic and disease characteristics

Demographic variables, stratification factors and other baseline characteristics will be summarized descriptively by treatment arm. The demographic variables age (metric), gender (female, male), ethnicity (Hispanic/Latino, not Hispanic/Latino) and race (American Indian/Alaska Native, Asian, Black/African American, Native Hawaiian/Other Pacific Islander, White) will be reported. Tumor size (T1-T2, T3) and nodal status (cytologically positive, radiologically or cytologically negative) are the two observed stratification factors by IxRS. Additionally, the tumor specific variables tumor stages (N-Stage; M-Stage) and tumor grading, and hormone receptor statuses (ER and progesterone receptor (PgR)), Ki67, ER status (Allred score), PEPI score as well as the Eastern Cooperative Oncology Group (ECOG) status will be analyzed.

Frequencies and percentages, means and standard deviations or medians and interquartile ranges will be given depending on the scale of the variable. Important protocol deviations

IPDs include inclusion and exclusion criteria, as well as selected variables belonging to additional relevant screening assessments, study treatment administration/dispensation, concomitant medication, primary endpoint, study treatment/randomization, study procedures/assessments, withdrawal/termination criteria and safety reporting. The IPDs are defined in a separate document listing all IPDs, their classification and additional details. IPDs will be summarized in total and by treatment arm and will be listed by study site, treatment arm and patient number.

3.5.4. Treatment disposition and exposure to study drug

Patient disposition and early discontinuation from treatment (GDC-0032/Placebo as well as letrozole) including reasons for discontinuation will be summarized by treatment arm.

Study medication intake including dose interruptions and dose reductions will be summarized overall and per treatment arm.

3.6. Primary endpoint evaluation

3.6.1. Primary endpoints

The co-primary efficacy endpoints are (1) tumor ORR (ICON: dataset RVIS, variable RRESPONS – CR, partial response (PR), stable disease (SD), Non-CR/Non-PD, PD, NE, no disease (ND)), centrally assessed by modified RECIST 1.1 criteria by breast MRI after completion of study drug, and (2) the rate of total pCR (tpCR - yes, no, not assessed) in breast and axilla, locally evaluated after completion of study drug and surgery, each in all randomized patients and PIK3CA MT patients. Information on PIK3CA mutation status (HistoGeneX: variable PIK3CAREsC) is assessed centrally.

The null- and alternative hypotheses for tumor ORR is as follows:

- H0: Tumor ORR is equal in patients receiving letrozole plus GDC-0032 compared to patients receiving letrozole plus placebo
- H1: Tumor ORR differs between patients receiving letrozole plus GDC-0032 compared to patients receiving letrozole plus placebo

The pCR endpoint results in the following null- and alternative hypotheses:

- H0: Total pCR rate is equal in patients receiving letrozole plus GDC-0032 compared to patients receiving letrozole plus placebo
- H1: Total pCR rate differs between patients receiving letrozole plus GDC-0032 compared to patients receiving letrozole plus placebo

3.6.2. Analysis for primary endpoints

The efficacy endpoint tumor ORR will be calculated by treatment arm in all randomized population and in PIK3CA MT population. Within each population, summary tables will be given and the ORR for the two treatment arms will be compared at a two-sided alpha of 16% using a Cochran Mantel-Haenszel test, stratified by tumor size and nodal status. The efficacy endpoint pCR rate will also be calculated and compared at a two-sided alpha of 4% based on the same analytical approach as ORR. The two alpha values account for a family-wise type I error rate of 20% for each population (all randomized patients and PIK3CA MT patients).

Patients with early study termination and hence missing efficacy outcome (ORR or pCR), as well as patients who are NE for MRI by central review (ORR only) will be included and considered as non-responders in the analysis.

3.6.3. Sensitivity analysis for primary endpoints

As sensitivity analysis for the primary efficacy endpoints, according analyses are repeated based on the PP population.

3.7. Secondary endpoint evaluation

3.7.1. Secondary endpoints

As secondary efficacy endpoints (1) tumor ORR (ICON: dataset RVIS, variable RRESPONS – CR, PR, SD, Non-CR/Non-PD, PD, NE, ND), centrally assessed by modified RECIST 1.1 criteria by breast MRI after completion of study drug, and (2) the rate of total pCR (tpCR - yes, no, not assessed) in breast and axilla, locally evaluated after completion of study drug and surgery, both are evaluated in PIK3CA WT patients.

Furthermore, secondary efficacy endpoints contain tumor overall ORR (CR, PR, SD, PD, not measurable/not assessed), locally assessed by modified RECIST 1.1 criteria by clinical breast examination (CaPalpOverResp), mammography (CaMammoOverResp), and breast ultrasound (CaSonoOverResp), after completion of study drug evaluated in all randomized patients and separately by PIK3CA mutation status.

Additionally, (1) change in Ki67 values (VHIO: variable Ki67ResN), centrally assessed, from baseline to Week 3, baseline to surgery, and Week 3 to surgery, (2) PEPI score (for relapse-free survival and breast cancer-specific survival, derived – classified into risk groups according to Ellis et al 2008 as PEPIR and PEPIB, respectively), at surgery, and (3) change in enhancing tumor volume (ICON: dataset VLES, variable TSHOLD1 - metric), centrally evaluated using breast MRI, from baseline to surgery, are considered as secondary efficacy endpoints in all randomized patients and in each of the PIK3CA mutation cohorts.

Last, different definitions of pCR, locally assessed after completion of study drug and surgery, are evaluated in all randomized patients and in each of the PIK3CA mutation cohorts. Included are the following possibilities: a) ypT0, ypN0 (according levels for

ypTStage and ypNStage), and b) ypT0/is, ypNX (breast pCR as nodal stage is not considered; bpCR - yes, no, not assessed).

3.7.2. Analysis for secondary endpoints

The two secondary efficacy endpoint measures in PIK3CA WT population will be summarized by treatment arm and will be analyzed analogous to the primary efficacy endpoints. Information on PIK3CA mutation status (HistoGeneX: variable PIK3CAREsC) is assessed centrally. Patients with early study termination and hence missing efficacy outcome, as well as patients who are NE for MRI by central review will be considered as non-responders in the analysis.

The further endpoint measures will be summarized by treatment arm and will be compared between the two treatment arms within each population based on appropriate statistical analyses: locally assessed ORR will be compared using a Cochran Mantel-Haenszel test, stratified by tumor size and nodal status within each method; change in Ki67, PEPI score and change in enhancing tumor volume will be compared by appropriate regression analysis models (depending on the distribution of the variables), e.g. logistic regression models, adjusted for tumor size and nodal status. For each of the different definitions of pCR, comparisons between treatment arms will be done by Cochran Mantel-Haenszel test, stratified by tumor size and nodal status.

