2.4. Number of subjects - sample size estimation

This study is designed for testing the effect of GDC-0032 on the two co-primary endpoints in all enrolled patients and in the PIK3CA MT patients and plans to enroll 330 patients in total. Assuming the PIK3CA mutation status will not be available (unknown) for approximately 10% of the patients and the prevalence of PIK3CA MT is 40%, there will be approximately 120 patients in the PIK3CA MT cohort.

Given that the PIK3CA mutation status is not a stratification factor for randomization, there might be a possible imbalance between treatment arms within the PIK3CA MT cohort, which may reduce the statistical power in this cohort. To ensure the study provides sufficient statistical power even when the treatment assignment is imbalanced, the sample size was calculated based on a conservative scenario by assuming that the treatment assignment imbalance in PIK3CA MT is 40% vs. 60%. The sample size was calculated based on a χ^2 -test using continuity correction (Ury and Fleiss 1980).

To control an overall, two-sided, family-wise error rate under 20% for each analysis population, we use a two-sided significance level of 16% and 4% for the co-primary endpoints MRI ORR, and pCR, respectively.

Assuming 10% of the patients are unevaluable for the MRI ORR, approximately 300 enrolled patients and 108 patients in the PIK3CA MT cohort will be evaluable for analyses. This sample size allows us to detect an absolute percentage increase of 24% in MRI ORR rate in the letrozole plus GDC-0032 arm (64%) versus the letrozole plus placebo arm (40%; Smith et al. 2005; Ellis and Ma 2007) in the PIK3CA MT cohort at 80% power and 16% two-sided significance level. The minimal detectable difference for ORR is approximately 15%.

Assuming that all patients are evaluable for pCR (i.e., approximately 330 enrolled patients and 120 in the PIK3CA MT cohort), this sample size provides 80% power to detect an absolute percentage increase of 18% in pCR in the letrozole plus GDC-0032 arm (19%) versus the letrozole-only arm (1%, Smith et al. 2005; Ellis and Ma 2007) in the PIK3CA MT cohort at the 4% two-sided significance level. The minimal detectable difference for pCR rate is approximately 13%.

The study is considered positive if at least one population shows a statistically significant result regarding the co-primary endpoints.

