3.1.2. Missing data

Subjects may have missing specific data points for a variety of causes. In general, data may be missing due to a missed visit, non-evaluability of a specific clinical measurement at its planned clinical visit or a subject's early withdrawal from study. The general procedures outlined below describe what will be done when a data point is missing.

3.1.2.1. *Imputations of missing data*

Generally, only evaluable measurements are considered for the analyses. No values are imputed for missed or non-evaluable visits. In case of primary and secondary efficacy endpoints possible specific requirements are stated in the according analysis sections.

3.1.2.2. *Partial dates*

Partially incomplete dates (day or day/month missing) will be imputed for dates related to AEs, to concomitant medication and medical history. Completely missing dates and missing years will not be imputed.

For DOB imputed dates will be used to derive the age of the patients since only month and year are captured due to regulatory reasons in some participating countries. DOB must not

have missing month information and hence, missing months will not be imputed. DOB will be imputed as described in the following table:

	Missing	Impute	Exception
DOB	Day	15	--

Dates belonging to AEs and concomitant medication will be imputed as described in the following table:

	Missing	Impute	Exception
Start date	Day	01	Date of first dose of study drug if imputed date would be prior to date of first dose of study drug
	Day/Month	01JAN	Date of first dose of study drug if imputed date would be prior to date of first dose of study drug
Stop date	Day	Last day of the month	Patient EOS date if the imputed date would be after patient EOS date
	Day/Month	31DEC	

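### Non-evaluable patients count as non-responders for central MRI ORR and total pCR only; the stated default drops them from local ORR, ypT0 ypN0 and breast pCR, and MRI ORR is powered on a different denominator from its analysis

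*SAP*

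**What the plan says.** **General rule.** SAP 3.1.2.1: "Generally, only evaluable measurements are considered for the analyses". Missed or non-evaluable visits are not imputed. For primary and secondary efficacy endpoints, any departure from this is to be found in the section that analyses them.

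**Where a departure is stated.** SAP 3.6.2 says that patients with early study termination and a missing ORR or pCR, and patients not evaluable on central MRI (ORR only), "will be included and considered as non-responders in the analysis". The first paragraph of 3.7.2 repeats this for central MRI ORR and total pCR in PIK3CA WT patients.

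**Where none is stated.** The second paragraph of 3.7.2 begins "The further endpoint measures will be summarized by treatment arm and will be compared between the two treatment arms within each population". It names stratified CMH tests for local ORR and for the other pCR definitions, and gives no rule for patients without an assessment. Section 3.7.1 shows that such patients are expected: local ORR has a category for not measurable or not assessed, and breast pCR is coded "bpCR - yes, no, not assessed".

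**Population.** Section 3.3.1 puts secondary analyses in the ITT population, and 3.7.1 evaluates these endpoints in all randomized patients.

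**Sample size.** SAP 2.4 assumes 10% unevaluable for MRI ORR, so that "approximately 300 enrolled patients and 108 patients in the PIK3CA MT cohort will be evaluable for analyses", and claims power for 40% against 64% "in the PIK3CA MT cohort at 80% power and 16% two-sided significance level". For pCR it assumes that every patient is evaluable (330 in all, 120 PIK3CA MT).

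**The concern.** The three pCR definitions are nested: ypT0 ypN0 lies within total pCR (ypT0/is ypN0), which lies within breast pCR (ypT0/is, any nodal status). Readers will compare their rates directly, and will likewise compare MRI ORR with ORR by ultrasound, palpation and mammography. If one member of each set counts unassessed patients as failures and the others leave them out, part of any difference comes from the denominator and not from the definition or the imaging method.

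The plan also pulls two ways on the same endpoints: the missing-data default removes patients, while the population statement includes everyone randomized. A programmer could defend either denominator, and the choice could then be made after unblinding.

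The sample-size text has a related mismatch for MRI ORR. It removes the unevaluable patients, whereas the primary analysis keeps them as failures. The stated power therefore describes a different calculation from the planned test.

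**Working it through.** **1. Tracing one patient.** Take a randomized patient who leaves the study without surgery.

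| Endpoint | Governing text | Status |
|---|---|---|
| Total pCR | 3.6.2 (3.7.2 first paragraph for WT) | failure, in the denominator |
| ypT0 ypN0 | 3.7.2 second paragraph has no rule, so 3.1.2.1 | absent |
| Breast pCR | as above | absent |

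The same applies to a patient with no usable imaging at Week 16: a failure for central MRI ORR, absent from local ORR.

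**2. When the stricter pCR rate prints higher.** Let N be randomized, e assessed, b total pCRs, and a those that are also ypT0 ypN0 (a ≤ b). The printed rates are a/e and b/N, and a/e > b/N whenever a/b > e/N. The order reverses once the share of total pCRs that are ypT0 exceeds the share of patients assessed. Illustration (assumed counts): N = 165 per arm, e = 148, a = b = 10. Then e/N = 0.897 and a/b = 1, so ypT0 ypN0 prints 10/148 = 6.8% and total pCR 10/165 = 6.1%.

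**3. Size for a response rate.** Borrow 40% and 64% from 2.4 as rates among assessed patients and assume an equal share q not assessed in each arm. Counting them as failures multiplies each rate by (1 − q):

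| q | Rates | Difference |
|---|---|---|
| 0 (evaluable only) | 40.0% vs 64.0% | 24.0 points |
| 5% | 38.0% vs 60.8% | 22.8 |
| 10% | 36.0% vs 57.6% | 21.6 |
| 20% | 32.0% vs 51.2% | 19.2 |

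**4. MRI ORR power.** Inputs from 2.4: two-sided alpha 16% (z = 1.405), 40% vs 64%, PIK3CA MT cohort split 40:60, chi-square with continuity correction. Let n be the control-arm size, k the ratio active/control, d the difference and p̄ the pooled rate. The effective size n′ solves

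n = (n′/4)·[1 + √(1 + 2(1 + 1/k)/(n′d))]²,

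and power = Φ{[d − z√((1 + 1/k)p̄(1 − p̄)/n′)] / √([p₁(1 − p₁) + p₂(1 − p₂)/k]/n′)}.

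- *The plan's figure.* N = 108, n = 43.2, k = 1.5, d = 0.24, p̄ = 0.544, n′ = 36.5: (0.24 − 0.1495)/0.1038 = 0.872, power **80.9%**. The stated 80% reproduces.
- *Analysis of 3.6.2, with 40% and 64% among evaluable patients and 10% unevaluable per arm.* N = 120, n = 48, rates 36% vs 57.6%, d = 0.216, p̄ = 0.4896, n′ = 40.6: (0.216 − 0.1423)/0.0984 = 0.749, power **77.3%**. At 1:1 it is 78.9%. At 40:60 without the correction it is 82.7%. With the correction, 80% needs about 130 PIK3CA MT patients at 40:60, or 124 at 1:1.
- *Analysis of 3.6.2, with 40% and 64% already all-patient rates.* N = 120, n = 48, d = 0.24, n′ = 41.3: (0.24 − 0.1406)/0.0976 = 1.019, power **84.6%**.
- *Unequal unevaluable shares* (assumed, control/active, rates among evaluable, 40:60, corrected): 10%/5% gives 86.6% and 10%/15% gives 65.4%.

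**5. pCR.** Section 2.4 removes nobody. The corrected formula at N = 120, 1% vs 19%, alpha 4% gives 79.1% with 40% of patients on control and 84.1% with 60% on control, consistent with the stated 80%.

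**The case against.** **No exclusion is written in 3.7.2.** The dropping of patients is inferred from 3.1.2.1, and the ITT statements point the other way. For ypT0 ypN0, 3.7.1 refers only to stage levels and lists no unassessed category. This is fair, and the claim should be put as what a literal reading produces. It does not remove the problem. Membership of the ITT population does not say how to code a missing outcome; 3.1.2.1 does. If that reading is rejected, there is no rule at all.

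**The reversal example is contrived.** It needs about 10% of patients without pathology (17/165), although 2.4 assumes all are evaluable for pCR, and it needs every total pCR to be ypT0. This stands as to size. The example shows that the order can reverse, not that it will. Unequal denominators arise with any missing pathology.

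**Evaluable-only analysis inflates the type I error.** A reader might infer this, and the documents do not support it. Assume a common rate of 36% among all randomized, 5% vs 15% not assessed, and 165 per arm: evaluable-only then rejects about 12% of the time at a nominal 5%. But assume a common 40% among assessed patients with the same missingness, and the non-responder rule also rejects about 12%. The figure only restates which denominator was taken as true, and the 5%/15% split appears nowhere in the plan.

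**The power shortfall is small and conditional.** This also stands. It needs the continuity correction, a deliberately conservative 40:60 split, and 40% and 64% read as rates among evaluable patients. Section 3.6.2 names a CMH test and mentions no correction. Section 2.4 also allows a larger sample if more patients than assumed are unevaluable for MRI.

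**Conclusion.** The main point holds. A stated default, combined with an exception written for only two endpoints, gives local ORR, ypT0 ypN0 and breast pCR a different denominator from central MRI ORR and total pCR, and conflicts with placing them in all randomized patients. With 5% to 20% unassessed equally in both arms (assumed), a 24-point difference among assessed patients becomes 22.8 to 19.2 points on the other rule. The co-primary endpoints have their own rule and are not affected by this gap, so the point should be fixed but does not threaten the main result.

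The secondary point holds for MRI ORR only. The stated 80% is correctly calculated for 108 evaluable patients, but 3.6.2 analyses about 120. The matching power is about 77% or about 85% at 40:60 with the correction, depending on what 40% and 64% mean, which the plan does not say. A reader might conclude that the trial is underpowered at 77%; the documents do not support any single replacement figure. Nor does the mismatch extend to pCR, which is sized on all patients.

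**What to change.** **Section 3.7.2.** Apply the rule of 3.6.2 to local ORR (each method), ypT0 ypN0 and breast pCR: all randomized patients of the population in question stay in the denominator, and not assessed, not measurable or no surgery counts as non-response. Show the evaluable-only result as supportive. Word the rule by missing outcome and not only by early termination, because 3.6.2 as written does not cover a patient who completes the study with total pCR not assessed. Add a cross-reference in 3.1.2.1.

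**Section 2.4.** State whether 40% and 64% are rates among evaluable or among all patients, and restate MRI ORR power on about 120 PIK3CA MT patients accordingly: about 77% in the first case (10% unevaluable in each arm, 40:60, corrected; about 79% at 1:1; about 83% at 40:60 uncorrected), about 85% in the second (40:60, corrected). The pCR paragraph needs no such restatement.

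**Cost.** Wording only, with no new data. Printed secondary rates become slightly lower, and the stated MRI ORR power may become slightly less favourable.

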3.8. Safety endpoint evaluation

3.8.1. Safety endpoints

Safety endpoints will be assessed through summaries of AEs, changes in laboratory test results and vital signs in all treated patients.

3.8.2. AEs and SAEs

Verbatim descriptions of AEs will be mapped to thesaurus terms (Medical Dictionary for Regulatory Activities (MedDRA) v19. 1). Only treatment-emergent AEs, hence, AEs outlined during protocol treatment period (on or after the first dose of study drug until 30 days after the last dose of study drug or until the end of study visit, whichever occurs later) or after this period, in case of deaths, serious adverse events, or other adverse events of concern deemed related to prior study drug treatment or study procedures, will be tabulated.

All AE data will be given by System Organ Class (SOC), preferred term (PT) and grade and will be summarized overall and by treatment arm. Additionally, serious AEs, deaths, AESIs (protocol defined – based on type and severity of AE or laboratory data), as well as AEs at NCI CTCAE v4.0 Grade 3 to 4 and Grade 5 and AEs leading to discontinuation, modification (i.e. reduction) or delay (i.e. interruption) of treatment will be summarized separately. Furthermore, AE data will be listed by study site, patient number, treatment arm, date of first dose of study drug, onset and resolved study day, seriousness, duration, severity, outcome and the relationship to study drug to understand the cumulative incidence as well as the time

to onset of first event when treated with GDC-0032+letrozole. The time to AE of special interest (time from first dose of study drug to first AE of special interest) will be shown graphically.

3.8.3. Laboratory data and vital signs

For relevant laboratory data (ALT, AST, bilirubin, calcium, glucose, hemoglobin, platelets, serum creatinine, white blood cells and HbA1C – all metric) shifts from baseline to minimum and maximum NCI CTCAE v4.0 grades will be given. Vital sign data (heart rate, blood pressure, and temperature – all metric) will be summarized in total and by treatment arm. Abnormal ECG data (based on BioTelemetry Research (BTR) data) will be listed.

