3.2. Types and timepoints of analyses

3.2.1. Main analyses

The main analysis used for preparing the Top Line Results (TLR) will be done after all patients underwent their post-surgery visit or dropped out of the study early and after clinical database closure and data management review.

The following data were not captured in the clinical database, but were assessed and/or gathered by external vendors:

- Response by centrally assessed MRI
- PIK3CA mutation status
- Data on KI67, ER status (Allred score) and expression of biomarkers
- PTEN (phosphatase tensin homolog)

- MRI volume
- ECG data

External vendor data available, received and checked by ABCSG prior to clinical database closure will be examined for the main analysis. After clinical database closure unblinding will occur at ABCSG with randomization information received from the IxRS vendor.

ABCSG will receive additional information regarding the concentration of GDC-0032 and letrozole for the pharmacokinetic, pharmacogenetic and biomarker endpoints after unblinding. The final analysis will be performed after all external vendor data are available, received and checked by ABCSG.

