3.3.3. Safety population

Safety analyses will be based on the safety (SAF) population and include all randomized and treated patients (patients who received at least one dose of study treatment). Patients will be analyzed according to the treatment actually received. Hence, randomized patients who wrongly received active drug at any time point will be included in the experimental arm in the SAF population.

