3.11. Listings

To review the snapshot clinical data for a patient, in case a safety event occurred, additional patient summary listings will be performed. For the following categories listings may be presented: demographics, medical history, history of primary breast cancer, surgery, physical examination, vital signs, radiological examinations, hematology, chemistry, electrolytes, DLCO, GDC-0032/placebo administration, letrozole administration, concomitant medication, treatment completion and surgery at treatment completion.

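### ECG is reported only as a listing of abnormal readings, with no count by arm and no number assessed (minor; one extra table would close it)

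*SAP*

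**What the plan says.** Section 3.8.3 covers laboratory data, vital signs and ECG, and gives each its own kind of output.

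- Laboratory data, for ten named parameters: "shifts from baseline to minimum and maximum NCI CTCAE v4.0 grades will be given".
- Vital signs: "Vital sign data (heart rate, blood pressure, and temperature – all metric) will be summarized in total and by treatment arm".
- ECG: "Abnormal ECG data (based on BioTelemetry Research (BTR) data) will be listed".

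Section 3.2.1 includes ECG among the data gathered outside the clinical database and adds: "External vendor data available, received and checked by ABCSG prior to clinical database closure will be examined for the main analysis". Section 3.3.3 sets the population: "Safety analyses will be based on the safety (SAF) population and include all randomized and treated patients", analysed by the treatment actually received. Section 2.1.3 makes the safety objective a comparison of the two arms. The measures named for it there, and in section 3.8.1 ("Safety endpoints will be assessed through summaries of AEs, changes in laboratory test results and vital signs in all treated patients"), do not include ECG.

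**The concern.** A listing restricted to abnormal readings shows cases without the patients they came from. A patient with a normal ECG and a patient with no ECG look the same in it, because neither appears. Nor does the plan say that the listing will be counted by arm. In a placebo-controlled trial with a comparative safety objective, the reader wants to know how many patients per arm had an abnormal reading, out of how many assessed, and whether the abnormality was new on treatment. The stated output answers none of these directly, although the vendor data would be in hand. What is at stake is the completeness of the safety report.

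**Working it through.** The SAP gives no ECG figure to reproduce, so this is a check of the text plus one identity.

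**Where ECG appears.** Apart from a glossary entry for the ECG vendor, the SAP mentions ECG in two places: the vendor-data list in section 3.2.1 and the listing sentence in section 3.8.3. Section 3.11 names 16 categories for optional patient listings ("For the following categories listings may be presented"), and ECG is not one of them. The sentence in 3.8.3 is therefore the only planned ECG output in this document.

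**Comparison within 3.8.3.** Of the three data types, vital signs get a summary in total and by arm, and laboratory data get grade shifts from baseline. Both are aggregate displays. ECG alone gets only individual records.

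**What the missing denominator does.** For one arm, let x be the number of patients with an abnormal post-baseline ECG, n the number with an evaluable post-baseline ECG, and N the number in the safety population. A reader with the listing and the randomization code can recover x and knows N, but not n. The rate then available is

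x/N = (x/n) × (n/N).

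This is the rate among assessed patients multiplied by the fraction assessed. Comparing x/N between arms matches comparing x/n only if n/N is the same in both arms. The listing gives no way to check that, because n is never reported. If nearly all patients were assessed in both arms, n/N is close to 1 and little is lost. If ECGs were done mainly on clinical indication, n/N could differ with toxicity. The SAP does not show which case applies.

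**Baseline status.** If abnormal baseline readings are listed, a patient with no baseline entry may have had a normal ECG or none. Without a shift display, new and pre-existing abnormalities cannot be reliably separated.

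**The case against.** The case for leaving the text alone is substantial.

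- ECG is not a named endpoint in section 2.1.3 or 3.8.1, so a listing is a stated choice and breaks no commitment. This stands and limits the point to an improvement.
- Abnormalities reported as adverse events are summarized by system organ class, preferred term, grade and arm under section 3.8.2. This also stands. It leaves out only readings not reported as events.
- A listing can be counted by arm after unblinding. That is true for the numerator; it does not supply the number assessed.
- The ECG schedule is not shown, and the table would be hard to read if ECGs were done only on indication. This stands, and the fix is conditional for that reason.
- A list of planned outputs appears in the glossary and might hold such a table. Its content is unknown, and section 3.8.3 does not refer to it.

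Two stronger readings are tempting, and the document does not support them. A reader might infer that electrolytes other than calcium were wrongly left out of the shift tables, since section 3.11 lists them separately ("hematology, chemistry, electrolytes, DLCO"). But section 3.8.3 prespecifies the laboratory data considered relevant, and the SAP does not show which other electrolytes were collected. A reader might also infer that the laboratory shifts will not be shown by arm, because that sentence does not say so. Sections 2.1.3 and 3.3.3 already make safety outputs treatment-based, so this is an omitted detail of wording. The same reasoning does not rescue the ECG output, because splitting an abnormal-only listing by arm still yields no number assessed.

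**Conclusion.** The point holds as a minor one. The SAP plans no by-arm count of ECG abnormalities and no number assessed, although its safety objective is comparative and the vendor ECG data are among those expected for the analysis. The conclusion rests on this document alone and assumes that no unseen output list supplies the table. The value of the change also depends on post-baseline ECGs existing, preferably on a schedule. No size can be given, because the SAP holds no ECG rates or evaluable numbers. A reader might infer that an ECG signal would go undetected. The document does not support that, since reported events are still compared by arm. Efficacy conclusions are unaffected.

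**What to change.** In section 3.8.3, where post-baseline ECGs exist, add one table for the safety population, by treatment arm and in total. It should give (a) the number of patients with an evaluable post-baseline ECG and (b) the number of those with an abnormal reading. If readings were scheduled, present it as a shift from baseline to worst post-baseline reading. Keep the listing as support. If ECGs were done only when clinically indicated, say so in a footnote, because the counts would then partly reflect who was tested.

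The cost is a sentence of SAP text and one table built from data that section 3.2.1 already expects from the vendor. No new assessments are needed.
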